### 6.6.3 Vital Signs and Weight

Vital signs (body temperature, respiratory rate, heart rate, systolic and diastolic blood pressure, weight and BMI) will be summarized by cohort at each scheduled visit. The actual value and change from Baseline to each post-baseline evaluation will be summarized for vital signs. Height at baseline will be used to calculate BMI.

By-subject listings of vital sign measurements will be presented in data listings.

#### **6.6.4 Electrocardiogram**

Heart rate, PR, QRS, QT, and QTcF will be summarized by cohort at each scheduled visit. The actual value and change from Baseline to each post-baseline evaluation will be summarized for ECGs. A tabulation of the overall ECG interpretation (normal, abnormal not clinically significant, or abnormal clinically significant) will also be presented.

All ECG data for each participant will be provided in data listings.

#### **6.6.5 Concomitant Medications**

Concomitant medications will be coded using the WHO Drug Dictionary. Prior and concomitant medications will be grouped by Anatomical Therapeutic Classification (ATC) and PT.

Prior medications are those medications that were stopped before first STAR-0215 administration. Concomitant medications (treatment period) are medications that are ongoing before baseline or taken at least once after STAR-0215 administration. Medications stopping on the same day as first STAR-0215 administration will be considered concomitant medications.

Run-In period medications are those that began between the date of the Screening Run-In visit and the first STAR-0215 administration date.

If a medication end date is partial, the month or year will be compared to STAR-0215 administration start date. If a medication date is missing, or partially missing, and it cannot be determined whether it was taken on or after STAR-0215 administration, it will be considered a concomitant (treatment period) medication.

Prior, Run-In Period, or Concomitant(Treatment period) medications will each be separately tabulated by Anatomic Therapeutic Class (ATC) and preferred term.

The use of medications will be included in by-subject data listing, designated as Prior, Run-In period, or Concomitant.

HAE medications will be summarized for prior usage, Run-In, and treatment period (based on definitions above). HAE medications will be determined by ATC codes ATC4=B06AC("DRUGS USED IN HEREDITARY ANGIOEDEMA") medication with an indication of 'HAE Attack' (per EDC) will also be summarized.

The use of HAE medications will be included in by-subject data listing, designated as Prior, Run-In period, or Treatment period medication.

## 7 CHANGES TO [REDACTED]

Protocol text related to Section 2.5 [REDACTED] was revised: due to fast enrollment each [REDACTED] will include additional participants and available [REDACTED] data.

Otherwise, there have been no changes between the protocol-defined statistical analyses and those presented in this statistical plan.

A [REDACTED] will take place when the first 16 participants dosed have completed treatment follow-up. Separate analyses will be performed for the “initial 16 participants’ and for all cumulative data at the time of the data cut-off.

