9.6. Efficacy Analysis

Unless otherwise specified, all analyses of HAE attack data will be presented similarly during the Run-In and treatment periods using the Efficacy Analysis Set. Data will be summarized for all investigator-confirmed HAE attacks.

The frequency and duration of HAE attacks will be presented with descriptive statistics overall and by participant. The following categories will be presented for attack duration: shorter than 12 hours, 12 to 24 hours, 24 to 48 hours, and longer than 48 hours.

Attack severity categorized as Mild, Moderate, or Severe will be presented overall and by participant.

The number and type of on-demand therapies used to treat HAE attacks will be summarized.

The proportion of HAE attack-free participants during the treatment period will be summarized.

The time normalized number of investigator-confirmed HAE attacks per month (attack rate) will be presented at 4-week intervals and at the end of the study. The mean monthly rate and 95% confidence interval will be presented.

To assess HAE attacks within a participant, the actual and percentage change from baseline (Run-In period) in monthly attack rate with respect to on-treatment attack rate will be calculated. The mean change and 95% confidence interval will be presented.

The proportion of participants with a clinical response to treatment will be presented in increments as greater than or equal to 40%, 50%, 60%, 70%, 80%, 90%, and 100% reduction of HAE attacks relative to baseline will be presented.

Time to first HAE attack after first and last dose of STAR-0215 will be presented using Kaplan-Meier estimates.

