**Signature:**

**Email:**

## MODIFICATION HISTORY

Current Version	Date	Amended by	Summary of Changes from previous version	Reason
1.0	11Jan2024		Original document	
2.0	05Apr2024	██████████ ██████████	
 
• Additional swimmer/Banerjee plot
 
• Additional intervals (3 and 6 months from Baseline) for HAE rate and incidence
 
• Repeating some analysis for participants who have completed intervals
 
• HAE attack rate for sub-categories of HAEs (severity or rescue medication)
 
• PK analysis repeated for treatment-emergent ADA status
 
• Adding definitions for treatment-emergent, treatment induced, and treatment boosted ADA status
 
	
Some additional HAE attack and PK analysis was performed with IA1, formally documenting this analysis in the SAP.
 
Adding sub-categories of HAEs based on 'administrative analysis'.
 
ADA definition was already present in the shells.

3.0	09Aug2024	██████████ ██████████	IA3 is added.	Client decision to perform analysis once the initial 16 participants completed.

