### 6.2.4 Multiple Comparisons/Multiplicity

No adjustments for multiplicity will be made.

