### 6.4.1 Change from Baseline in Monthly HAE attack rate

HAE attack rate will be expressed as the number of unique investigator-confirmed HAE attacks per month. Only unique (non-overlapping) HAE attacks will be counted; attacks are considered overlapping when a start date falls within 24 hours of an earlier attack's end date. The HAE attack rate will be calculated as:

$(\text{number of HAE attacks} / \text{duration of evaluation period in days}) * 30.4375$ ; where the duration of participants' run-in period and post-treatment follow-up periods is defined in [Section 9.1](#) and [section 5.2 \(Treatment period\)](#).

Change from baseline (Run-In period) to on treatment HAE attack rate, will be summarized by the absolute and percentage change from Baseline. Descriptive statistics (mean, median, standard deviation, Q1, Q3, minimum and maximum values) and 95% CI will be presented. The proportion of participants with a clinical response to treatment will be presented in increments as greater than or equal to 50%, 70%, and 90% reduction of HAE attacks.

A plot of individual participant's HAE attacks over time will display duration and severity by cohort. The plot will begin in the run-in phase through the last HAE assessment. The scheduled dose(s) of each cohort will be represented with dotted-lines. This plot will also be created by HAE attack location or overall cohort plot (combining participants).

HAE attacks per month (attack rate) will be presented at 4-week intervals (28 Days) from treatment start; first dose period, and 3 and 6 month intervals following last dose; and the first 3 and 6 months from Baseline (from initial dose) will also be provided. The mean monthly rate, change from baseline, and 95% CI will be presented; percent change will also be presented for monthly rates. Additional analysis of participants who have completed each interval may be performed.

Analysis of overall HAE attack rate or certain intervals, will be performed on sub-categories of HAEs: by HAE severities Mild, Moderate, Severe, and Moderate or Severe; and those that required therapy (“rescue medication”).

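### SAP Section 7 wrongly says that only the interim revision departs from the protocol's analyses, and the analyses added in SAP v2.0 after trial data were analysed carry no post hoc label

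*SAP*

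**What the plan says.** Protocol 9.6 gives the time-normalised attack rate for all investigator-confirmed attacks, which "will be presented at 4-week intervals and at the end of the study", together with the actual and percentage change from Run-In to the on-treatment rate. It lists seven response thresholds.

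SAP 6.4.1 keeps the change from Run-In to on-treatment rate and the 28-day intervals. It then adds the first-dose period, 3 and 6 months after the last dose, "and the first 3 and 6 months from Baseline (from initial dose) will also be provided", and optional repeats in participants who completed an interval. It continues: "Analysis of overall HAE attack rate or certain intervals, will be performed on sub-categories of HAEs". The intervals meant are not listed.

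The SAP modification history, version 2.0 (05Apr2024), lists among its additions the 3- and 6-month-from-Baseline intervals, the completed-interval repeats, the sub-category rates, and PK by treatment-emergent ADA status. Its reasons include "Some additional HAE attack and PK analysis was performed with IA1, formally documenting this analysis in the SAP" and "Adding sub-categories of HAEs based on 'administrative analysis".

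SAP Section 7 mentions only the interim analyses, and then: "Otherwise, there have been no changes between the protocol-defined statistical analyses and those presented in this statistical plan". On multiplicity, SAP 6.2.4 says: "No adjustments for multiplicity will be made".

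**The concern.** Section 7 is where a reader looks to learn how the analysis departs from the protocol. If it denies departures that exist, a reader cannot separate what was planned before any data were analysed from what came later. The study is open label (SAP 2.4), and SAP 1.1 makes this text the basis for the results sections of the clinical study report. SAP 6.4.1 describes the protocol's analyses and most of the later ones in the same terms, with no exploratory or post hoc label.

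The monthly attack rate is the first-listed secondary efficacy endpoint, cohorts hold 4 to 12 participants, and interim results feed sponsor decisions (SAP 2.5). The stake is selective emphasis: a late window or sub-category could be reported as if it had been pre-specified.

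**Working it through.** The plan has no alpha, power or effect size to reproduce. The check is a comparison of texts, then of dates.

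**Step 1. Current SAP against current protocol**

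| Item | Protocol | SAP | In Section 7? |
|---|---|---|---|
| Attack-rate windows | 9.6: 4-week intervals, end of study, change from Run-In | 6.4.1: also first-dose period, 3 and 6 months after last dose, first 3 and 6 months from Baseline | No |
| Completed-interval repeats | None | 6.4.1, optional | No |
| Rates by attack type | None | 6.4.1: mild, moderate, severe, moderate or severe, rescue-treated | No |
| Response thresholds | 9.6: 40, 50, 60, 70, 80, 90, 100% | 6.4.1: 50, 70, 90% | No |
| Attack duration | 9.6: descriptive, overall and by participant | 6.4.3: each participant's longest attack | No |
| Plasma kallikrein activity | 9.7: descriptive statistics | 6.5.2: adds within-group p-values | No |

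Counts: added windows 1 + 2 + 2 = 5; sub-categories 5; thresholds dropped 7 − 3 = 4 (40, 60, 80, 100%).

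**Step 2. What can be dated**

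The v2.0 entry covers two of the five added windows (first 3 and first 6 months from Baseline), the completed-interval repeats, the sub-category rates and PK by treatment-emergent ADA. Its reasons say that additional HAE and PK analysis had already been run with IA1, and tie the sub-categories to an administrative analysis. SAP 2.5 describes such administrative analyses as ones that may monitor efficacy. So these items entered the SAP after analyses of trial data. The entry does not match each remaining item to a reason, and it says that the ADA definition was already in the table shells.

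The other three windows, the threshold cut, the longest-attack summary and the PD p-values appear in neither the v2.0 nor the v3.0 entry. They are undeclared in Section 7 but not shown to be late.

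**Step 3. Can a size be put on the late windows?**

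Illustration only, since the documents give no rates. Assumptions: participant rate = cohort rate × gamma variable (mean 1, CV 1); counts are Poisson(rate × days / 30.4375); baseline 2 per month; constant on-treatment rate of 0.5 per month, so the true reduction is 1 − 0.5/2 = 75%. Elapsed days in total and to the second dose are 250 and 83 (Cohort 2) and 194 and 27 (Cohort 3); n = 6; 20,000 simulated trials. Average reduction if the lowest window is quoted:

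| Windows compared | Cohort 2 | Cohort 3 |
|---|---|---|
| Overall plus all five added | 80.9% | 82.9% |
| Same, without the two v2.0 windows | 80.6% | 82.7% |
| Overall plus the two v2.0 windows only | about 78% | about 78% |
| Lowest of the protocol's own 28-day intervals | about 93% | about 92% |

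The two late windows add 80.9 − 80.6 = 0.3 and 82.9 − 82.7 = 0.2 points. Most of the apparent inflation comes from showing several intervals in six people, which the protocol already does. It is not a measure of this defect.

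**The case against.** The strongest reply is that little is hidden and most of it is allowed. The modification history states the additions, the date and the reasons. Protocol 9.2 lets the SAP be finalised up to database lock, and Protocol 9.11 lets it describe pre-planned exploratory analyses. Attack severity and attacks needing on-demand therapy are already protocol secondary endpoints. SAP 3.2 frames the rate endpoint as overall and per month, and 6.4.1 puts the Run-In to on-treatment change first. The 100% threshold over the whole period is in substance the attack-free proportion in SAP 6.4.2.

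All of that stands. It shows that the additions are permissible and disclosed in the front matter. It does not make the Section 7 sentence true or supply a label in the text from which the report will be written. The history is used here only as evidence of timing; the contradiction lies between the current SAP and the current protocol.

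A reader might infer more than the documents support:

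- **The late analyses were picked because they looked favourable.** The history shows that analyses were run before they were written in. It does not show selection on results.
- **All the added windows, and the threshold cut, followed interim data.** Only the items in the v2.0 entry are dated that way.
- **The sub-categories came from IA1.** They are tied to an administrative analysis, which the documents do not equate with IA1.
- **A 5% error rate is breached, or the late windows inflate the effect substantially.** SAP 6.2.1 disclaims formal hypothesis testing, 6.4.1 limits sub-categories to the overall rate or certain intervals, and Step 3 attributes only 0.2 to 0.3 points to the late windows under its assumptions.

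**Conclusion.** The Section 7 statement is wrong on the face of the documents. Six kinds of departure in efficacy and PD analysis go undeclared: windows, completed-interval repeats, sub-category rates, thresholds, duration summary and PD p-values. For the three of these in the v2.0 entry (the from-Baseline windows, the repeats and the sub-category rates), and for PK by treatment-emergent ADA, the SAP itself shows that analysis of open-label data came before documentation. The body carries no post hoc label.

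The consequence is limited. Efficacy is descriptive, no type I error is breached, and the primary safety objective is untouched. What changes is which results the study report may present as pre-specified. The conclusion rests on the texts and the version dates, not on the simulation or on any assumption about why the analyses were added.

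**What to change.** 1. Replace the Section 7 sentence with a list of every departure from the protocol-defined analyses, each with its date and reason.
2. Label the v2.0 additions (from-Baseline windows, completed-interval repeats, sub-category rates, PK by treatment-emergent ADA) as *post hoc, added in SAP v2.0 after review of trial data*. Use the label in SAP 6.4, the PK section, the table titles and the study report.
3. Restore the 40, 60, 80 and 100% response thresholds, or declare their removal.
4. State in SAP 6.4.1 that the lead efficacy summary is the all-attack change from Run-In over the whole Treatment Period (Day 168, 251 and 195 in Cohorts 1, 2 and 3), which the section already lists first, and that the other windows are supportive.

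The cost is SAP wording, table titles and a few table rows, with no new data. The downside for the sponsor is that the added analyses can no longer be presented as pre-specified.

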## 9 APPENDICES

### 9.1 Schedule of Assessments

**Table 6: Schedule of Assessments: Cohort 1**

Schedule of Assessments: Cohort 1																		
	Screen- ing	Run-In 	Treatment and Follow-up															
Study Day Window (days)	-56	-56 to -1	1		2	7 ±1	14 ±2	28 ±2	56 ±3	84 ±3	112 ±5	140 ±5	168  ±7 or ET					
			Pre	Post										±7	±7	±7	±7	±7 or ET
Study Assessments																		
Informed Consent	X																	
Inclusion/Exclusion Criteria	X																	
Medical History/ Demographics	X																	
FSH 	X																	
Virus Serology (HBsAg, HCV, and HIV)	X																	
C1-INH (level or function)	X																	
C4	X																	
Confirm Eligibility			X															

Schedule of Assessments: Cohort 1																		
	Screen- ing	Run-In 	Treatment and Follow-up															
Study Day Window (days)	-56	-56 to -1	1		2	7 ±1	14 ±2	28 ±2	56 ±3	84 ±3	112 ±5	140 ±5	168  ±7 or ET					
			Pre	Post										±7	±7	±7	±7	±7 or ET
STAR-0215 Administration			X															
Pregnancy Test 	S		U					S	S	S			S					S
12-Lead ECG 	X		X			X	X	X	X	X			X					X
Hematology 	X		X			X	X	X	X	X	X	X	X					X
Chemistry 	X		X			X	X	X	X	X	X	X	X					X
Coagulation 	X		X			X	X	X	X	X	X	X	X					X
Urinalysis 	X		X			X	X	X	X	X	X	X	X					X
Vital Signs 	X		X	X 	X	X	X	X	X	X	X	X	X					X
Physical Examination (including Height/Weight/BMI) 	X		X	X 	X	X	X	X	X	X	X	X	X					X
HAE Attack Information	X	Weekly contacts 	X	X	X	X	Scheduled site visits and weekly contacts on: Days (±1) 21, 35, 42, 49, 63, 70, 77, 91, 98, 105, 119, 126, 133, 147, 154, and 161											

Schedule of Assessments: Cohort 1																		
	Screen- ing	Run-In 	Treatment and Follow-up															
Study Day Window (days)	-56	-56 to -1	1		2	7 ±1	14 ±2	28 ±2	56 ±3	84 ±3	112 ±5	140 ±5	168  ±7 or ET					
			Pre	Post										±7	±7	±7	±7	±7 or ET
Pharmacokinetic Blood Sample			X	X 	X	X	X	X	X	X	X	X	X					
Pharmacodynamic Blood Sample (plasma kallikrein)	X		X	X 	X	X	X	X	X	X	X	X	X					
Immunogenicity (anti-drug antibody)			X				X	X	X	X	X	X	X					
 (serum/plasma)	X		X			X		X	X	X			X					
Transcriptomics (RNA PAXgene ® )	X		X			X		X	X	X			X					
Optional Pharmacogenetics/- omics (DNA PAXgene ® ) 			X					X		X			X					
			X					X	X	X	X	X	X					
Prior and Concomitant Medications	X	Weekly contacts 	X	X	X	X	Scheduled site visits and weekly contacts on: Days (±1) 21, 35, 42, 49, 63, 70, 77, 91, 98, 105, 119, 126, 133, 147, 154, and 161							X	X	X	X	X

Schedule of Assessments: Cohort 1																		
	Screen- ing	Run-In 	Treatment and Follow-up															
Study Day Window (days)	-56	-56 to -1	1		2	7 ±1	14 ±2	28 ±2	56 ±3	84 ±3	112 ±5	140 ±5	168  ±7 or ET					
			Pre	Post										±7	±7	±7	±7	±7 or ET
Adverse Events 	X	Weekly contacts 	X	X	X	X	Scheduled site visits and weekly contacts on: Days (±1) 21, 35, 42, 49, 63, 70, 77, 91, 98, 105, 119, 126, 133, 147, 154, and 161							X	X	X	X	X

Abbreviations: AE = adverse event; BMI = body mass index; C1-INH = C1-esterase inhibitor protein; CBC = complete blood count; ECG = electrocardiogram; ET = early termination; FSH = follicle-stimulating hormone; HAE = hereditary angioedema; HBsAg = hepatitis B surface antigen; HCV = hepatitis C virus; PD = pharmacodynamic; PK = pharmacokinetic; Pre = pre-dose; Post = post-dose; S = serum; U = urine.

**Note:** If a participant presents to the study site with symptoms of an HAE attack during the study (Screening through the 6 month follow-up after the last dose of STAR-0215) and it does not coincide with a scheduled site visit, HAE attack information, prior and concomitant medications, AEs, targeted physical examination, vital signs, and blood samples for C1-INH, PK (excluding Run-In period), plasma kallikrein, serum and plasma biomarkers, and immunogenicity (excluding Run-In period) should be collected during that unscheduled visit.

1 If a participant has an HAE attack during the Run-In period before Day 1, all signs and symptoms of the HAE attack must be resolved before dosing. A washout period for on-demand treatment is not required. The Run-In period may be extended after consultation with the Medical Monitor.

2 FSH testing is only performed if needed to confirm a postmenopausal state (i.e. no menses for 12 months without an alternative medical cause) in participants not using hormonal contraception or hormone replacement therapy.

3 Pregnancy testing performed only for participants of childbearing potential.

4 All 12-lead ECG assessments must be performed before blood sample collection. Assessment is to be performed after the participant has been in a supine position for at least 5 minutes.

5 The hematology assessment will be a CBC with differential.

6 The chemistry assessment includes total protein, albumin, glucose, alkaline phosphatase, bilirubin (total and direct), aspartate aminotransferase, alanine aminotransferase, gamma-glutamyl transferase, lactate dehydrogenase, uric acid, blood urea nitrogen, creatinine, calcium, sodium, potassium, chloride, carbon dioxide, phosphate, magnesium, cholesterol, triglycerides, and creatine phosphokinase.

7 The coagulation assessment includes international normalized ratio, activated partial thromboplastin time, and prothrombin time.

8 The urinalysis includes pH, glucose, ketones, blood, specific gravity, nitrite, protein, bilirubin, and microscopy (if urinalysis is abnormal).

- 9 Vital signs (including blood pressure, heart rate, respiratory rate, and body temperature) will be taken prior to blood sample collection and after the participant has been in a supine position for at least 5 minutes. Vital signs will be taken pre-dose within 4 hours of dosing and 4 hours ( $\pm 30$  minutes) post-dose.
- 10 Height collected at Screening only. Complete physical examinations will be performed at Screening and the post-dose timepoint on Day 1. All other physical examinations will be a targeted evaluation of general appearance, skin, abdomen, and cardiovascular and respiratory systems. The Day 1 post-dose physical examination will be performed at 4 hours ( $\pm 30$  minutes).
- 11 During the Run-In period, the weekly contacts will be conducted on Days ( $\pm 1$ ) -49, -42, -35, -28, -21, -14, and -7. HAE attacks will be collected from the time of informed consent.
- 12 On Day 1, PK and PD blood samples will be collected pre-dose and 4 hours  $\pm 15$  minutes post-dose.
- 13 Blood sample collection for pharmacogenetics/-omics testing is optional and requires additional participant consent.
- 14 All AEs will be recorded from the time of informed consent through the final study visit.
- 15 For participants who do enroll in the long-term open label extension study, this will serve as the final visit with end of study assessments.
- 16 Remote visits to collect concomitant medication and AE assessments including information regarding pregnancy and HAE attacks.
- 17 On-site visit to collect concomitant medication and AE assessments including information regarding pregnancy and HAE attacks.

